## Publications

Results will be presented at international conferences and published in international journals with an interest in CD, endoscopy and imaging. Positive as well as negative and inconclusive results will be published. Participating physicians are offered authorship based on each author's contributions to the work following the Vancouver recommendations. [name] is first author of the main study. Additional authorships, including the last author, as well as authorships for subsequent publications deriving from data collected according to this protocol are determined by the contribution of each author. Data are reported in accordance with the CONSORT guideline for non-inferiority and equivalence randomized trials.

## Economy

This study was initiated by the principal investigator and physicians from the participating centers. None of the physicians in the steering committee have conflicts of interest in regard to this study. Physicians from the participating centers will declare their conflicts of interest. Granted financial support will be deposited on a research account at the Hospital of Southwest Jutland ("ANDI-3", account number SVS.41.8-11.17220) under public audit.

The project has received funding by a grant from Aage og Johanne Louis-Hansens Fond (DKR 1 275 000) and an unconditional grant from Tillotts Pharma AG (DKR 200 000).

Applications for grants from the PhD Fund of the Region of Southern Denmark (DKR 610 000) and the Region of Southern Denmark Independent and Strategic Research Fund (DKR 400 000) have been submitted. We will apply for a faculty scholarship from the Graduate School of Health Sciences at the University of Southern Denmark (DKR 400 000) when other funding has been secured.

## BUDGET- OG FINANSIERINGSPLAN

Projekttitel: Feasibility of a non-invasive diagnostic algorithm in suspected Crohn's disease – a prospective comparison of pan-enteric capsule endoscopy versus ileocolonoscopy plus MR enterography or small-bowel capsule endoscopy										
Budgetpost	Enhed	Udgift	Antal	Samlet beløb	Region Syddanmarks ph.d.-pulje	Syddansk Universitet - Institut for Regional Sundhedsforskning	Region Syddanmarks pulje for Fri- og Strategisk Forskning	Aage og Johanne Louis-Hansens Fond	Andre fonde	
Aflønning										
[name], ph.d. års værk inkl. studieafgift	År	623.333,33	3	1.870.000,00	610.000,00	400.000,00	0,00	650.000,00	210.000,00	
Projektkordinator - deltidssat sygeplejerske	År	200.000,00	2	400.000,00	0,00	0,00	400.000,00	0,00	0,00	
Drift										
Pillcam Crohns (kamerapille)	Stk.	5.600,00	110	616.000,00	0,00	0,00	0,00	616.000,00	0,00	
Pillcam Patency capsule (selvoplosgelig testkapsel)	Stk.	500,00	20	10.000,00	0,00	0,00	1.000,00	9.000,00	0,00	
Bistand fra OPEN og statistiker				20.000,00	0,00	0,00	20.000,00	0,00	0,00	
Kurser og konгрesser				20.000,00	0,00	0,00	20.000,00	0,00	0,00	
Besøg ved udenlandsk forskningsenhed				30.000,00	0,00	0,00	0,00	0,00	30.000	
Udgifter til publikation				30.000,00	0,00	0,00	30.000,00	0,00	0,00	
Andet										
Patientbefordring				50.000,00	0,00	0,00	50.000,00	0,00	0,00	
I alt				3.046.000,00	610.000,00	400.000,00	521.000,00	1.275.000,00	240.000	
Total budget										kr 3.046.000,00
Fondene markeret med grønt har bevilget penge til projektet										

## Diagnostic procedures and definitions

### Diagnostic criterion for Crohn's disease

A single gold standard for the diagnosis of CD is not available. CD is a syndrome diagnosis based on a clinical evaluation and a combination of endoscopic, histological, radiological, and/or biochemical investigations. All patients included in this study have a clinical presentation suggesting CD, and findings consistent with CD with different modalities are outlined below.

### Pan-enteric capsule endoscopy

CE is carried out with the Pillcam Crohn's capsule (Medtronic, Dublin, Ireland). The following bowel cleansing regimen is used:

*Two days before CE:* Patients should avoid iron supplements and drink additional fluids (up to 2 L)

*The day before CE:* Light breakfast followed by clear liquid diet throughout the day.

0,5 L Plenvu and 1 L clear noncarbonated nonalcoholic liquid 18.00-19.00.

*The day of CE:* 0,5 L Plenvu and either 240 mg Imogas (simethicone) or 200 mg Minifom (dimethicone) 45-75 min. before capsule ingestion.

30 minutes after 2 mg Resolor (prucalopride) is administered with 0,1 L water. The capsule is ingested with a cup of water and either 240 mg Imogas (simethicone) or 200 mg Minifom (dimethicone).

In case the capsule has not reached the small bowel after 1 hour chewing gum is chewed for 15 min. x 2 and either 10 mg Metoclopramide or 20 mg Domperidone is administered.

1st boost (when the capsule reaches the small bowel): 1 sachet of Picoprep (sodium picosulphate, magnesium oxide, citric acid) in 150 mL water with either 240 mg Imogas (simethicone) or 200 mg Minifom (dimethicone). Drink additional 1 L of clear noncarbonated nonalcoholic liquid.

2nd boost (3 hours after 1st boost if capsule is still in the body): 1 sachet of Picoprep (sodium picosulphate, magnesium oxide, citric acid) in 150 mL water

with either 240 mg Imoges (simethicone) or 200 mg Minifom (dimethicone). Drink additional 1 L of clear noncarbonated nonalcoholic liquid. 3rd boost (2 hours after 2nd boost if capsule is still in the body): 20 mg Bisacodyl (Dulcolax) as suppository. A light meal can be ingested 2 hours after the 3rd boost or after excretion of the capsule.

CEs are analyzed by the primary investigator or a specialist in medical gastroenterology with experience in capsule endoscopy. The PillCam Reader Software from Medtronic is used for the analysis. Findings are reported in a standardized fashion according to the *Capsule Endoscopy Minimal Standard Terminology* (CEMST). It is recorded whether the capsule reaches the colon and anus. The transit times through the stomach, small intestine and colon are determined. Pathological findings are localized according to the time interval after capsule ingestion and the usual landmarks. The small intestine is divided into thirds based on the passage time. The colon is divided into five segments: Cecum, ascending colon, transverse colon, descending/sigmoid colon and rectum. The right and left flexures are used as landmarks for this subdivision. Disease severity in both small bowel and colon is assessed with the SES-CD and Eliakim score, while disease severity in the small intestine is furthermore assessed with the Lewis score.

#### *Findings at CE consistent with CD:*

- Multiple (> 3) erosions or aphthous ulcers
- Irregular ulcers or fissures
- Cobblestone pattern
- Luminal narrowing because of inflammation and/or fibrous stenosis

#### *CE report*

A full report including photo documentation is prepared and disclosed to the treating physician. The description must state the following findings:

- Is the procedure complete?
- Image quality (cleanliness level)
- Lesions consistent with CD
- Localization and severity
- Other pathology
- Clinical recommendation:

- 1) A complete procedure with sufficient quality and an unambiguous diagnosis requiring no additional examinations
- 2) Additional examinations recommended because of an incomplete procedure, poor image quality, ambiguous lesions or suspected malignancy

### *Complete procedure*

A capsule expelled from the rectum defines a complete CE procedure. An incomplete CE prompts additional examinations of the bowel segments not visualized.

### *Image quality*

The colon cleansing is graded on a 4-point scale: Poor (1): Large amount of fecal residue precludes a complete examination. Fair (2): Enough feces or turbid fluid to prevent a reliable examination. Good (3): Small amount of feces or turbid fluid not interfering with examination. Excellent (4): No more than small bits of adherent feces. A poor image quality prompts additional examinations.

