## Endpoints

*Primary endpoint:*

1. Diagnostic completeness, defined as the proportion of patients in each group achieving a complete gastrointestinal assessment and an unambiguous diagnosis after the first-line work-up strategy without need for supplementary examinations.

*Secondary endpoints:*

1. Feasibility of pan-enteric CE: Number of patients with suspected CD examined with pan-enteric CE and the number of ICs avoided
2. Additional examinations: Need for additional examinations in the two randomization arms
3. Safety: Number of severe adverse events, delayed or missed diagnoses
4. Time to diagnosis: Time from referral or first diagnostic procedure to a final diagnosis and treatment
5. Disease classification and medical treatments in the two randomization arms
6. Patient satisfaction: Difference in Gastrointestinal Endoscopy Satisfaction Questionnaire (GESQ) score
7. Costs: Expenditure on diagnostic procedures, treatment and loss of productivity
8. Artificial intelligence: Diagnostic utility of AI algorithms in detection of gastrointestinal pathology using pan-enteric CE – sensitivity, specificity, severity, prediction and impact on clinical decision making

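### Cleansing grade Fair is defined as unreliable, yet only poor quality triggers further examination and sufficient quality is tied to no grade

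*Protocol*

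**What the plan says.** The protocol's section on image quality for pan-enteric CE sets out a four-point cleansing scale. The two lower grades are "Poor (1): Large amount of fecal residue precludes a complete examination" and "Fair (2): Enough feces or turbid fluid to prevent a reliable examination". The two upper grades, Good and Excellent, describe residue that does not interfere or is minimal. The section ends with one consequence: "A poor image quality prompts additional examinations".

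The CE report section has a field labelled "Image quality (cleanliness level") and offers two clinical recommendations:

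- Option 1: "A complete procedure with sufficient quality and an unambiguous diagnosis requiring no additional examinations".
- Option 2: "Additional examinations recommended because of an incomplete procedure, poor image quality, ambiguous lesions or suspected malignancy".

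The section on a complete procedure says: "A capsule expelled from the rectum defines a complete CE procedure".

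Under Endpoints, the primary endpoint asks for a complete gastrointestinal assessment and "an unambiguous diagnosis after the first-line work-up strategy without need for supplementary examinations". Under Minimally invasive diagnostic work-up, a second expert countersigns lesions of interest, a committee settles disagreement between the two experts, and the treating physician then decides on diagnosis and further work-up.

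**The concern.** By the scale's own definitions, the line between an examination that can be relied on and one that cannot falls between grades 2 and 3. The stated trigger uses the name of grade 1. Grade 2 is therefore described as unreliable but is given no consequence, and the term that should exclude it, sufficient quality, is not defined.

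This bears on the primary endpoint because option 1 nearly restates it. Compared with not counting them, counting Fair studies as sufficient can only raise CE completeness, which favours a non-inferiority conclusion. The report is also issued during care. If capsule readers apply different thresholds, the grade can be rescored later, but nobody can then recover which examinations would have been ordered.

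**Working it through.** **Inputs.** The grade definitions and trigger come from Image quality, the two options from CE report, and the definition of completeness from Complete procedure. The planning rates are in Expected diagnostic completeness, and the 110 patients in the CE arm are in Sample size calculation.

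**Step 1: set the grades against the rules.**

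| Grade | Scale's own description | Named by the poor-quality trigger, read on the scale? | Stated to be sufficient? |
|---|---|---|---|
| Poor (1) | complete examination not possible | yes | not stated |
| Fair (2) | reliable examination not possible | no | not stated |
| Good (3) | no interference | no | not stated |
| Excellent (4) | minimal residue | no | not stated |

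Only Fair is both described as inadequate and left out of the trigger.

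**Step 2: see whether another condition catches a Fair study.** Option 1 has three conditions.

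- Completeness does not catch it, because expulsion alone defines a complete procedure.
- An unambiguous diagnosis does not necessarily catch it, because the capsule reader may find the visible lesions, or their absence, clear.
- Sufficient quality could catch it, but the term has no grade attached.

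An expelled, Fair-graded study with a clear reading can therefore be placed under option 1 without breaking any written rule.

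**Step 3: decide whether poor means the grade.** The scale and the trigger stand under one heading, and the report field equates image quality with cleanliness level. The grade reading is therefore the natural one, though not the only one.

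**Step 4: reproduce the planned completeness.** For the CE arm, 0.90 × 0.80 × 0.90 = 0.648, which the protocol states as 65%. The three factors are patients not withdrawn, complete examinations and diagnostic procedures. None is labelled as image quality. The last factor may or may not include inadequate cleansing, so the planning figure does not show whether Fair studies were expected to fail.

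**Step 5: express the size per study.** With all 110 CE-arm patients in the denominator, one study whose status turns on the reading of Fair moves CE completeness by 1/110 = 0.0091, or 0.9 percentage points. The protocol gives no rate of Fair grades, so this cannot be multiplied up to a total.

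**The case against.** The strongest reply is that the ordinary reading already excludes Fair from option 1. The two options read as complements, and a capsule reader who has graded a study as not reliably examinable would contradict that grade by calling it sufficient. On this view, poor is a plain adjective that covers both lower grades. The reading is defensible, and for that reason the gap is something the text allows rather than requires. It does not remove the point, because an endpoint-relevant term still has two reasonable readings.

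The second reply is that safeguards exist. The report must state the cleanliness level, so the treating physician sees a Fair grade and decides on further work-up. The report therefore informs the endpoint but does not settle it, and this stands. The expert committee helps less: it acts only when the two experts disagree, and it supplies no threshold when both pass a Fair study.

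Third, the background section on pan-enteric CE reports that diagnostic yield for Crohn's disease was unaffected although few patients took the full bowel preparation. That finding concerns preparation volume, not studies graded Fair, and the same section calls the preparation needed for sufficient image quality a significant limitation. It is still a reason to think that the effect may be small.

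Fourth, scoring rules for an endpoint can be left to a statistical analysis plan, which is not shown here. That plan could fix the scoring, but it could not reconcile a scale and a trigger that capsule readers use during care.

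A reader might go further and infer that Fair studies must be counted as complete, or that the trial loses power. The documents support neither. The first inference ignores the sufficient-quality condition and the physician's decision. The second needs a Fair rate that the protocol does not give, so any power figure would rest on an invented share.

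**Conclusion.** The point holds as an inconsistency in the protocol. Fair is defined as preventing reliable examination, the stated quality trigger carries the name of grade 1 only, and sufficient quality maps to no grade. An expelled study graded Fair can therefore be reported as needing no further examination and so count towards CE completeness.

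The size is unknown. The only figure the protocol supports is 0.9 percentage points per affected study, assuming that all 110 CE-arm patients are in the denominator. A study is affected only if it is graded Fair, meets the other conditions of option 1 and is followed by no further examination. The direction is clear, since leniency towards Fair can only raise CE completeness, but the practical effect may be small.

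**What to change.** Reconcile the Image quality and CE report sections so that the grade definitions, the poor-quality trigger and the term sufficient quality agree. Which grade prompts further examination in patient care is for the investigators to settle.

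Separately, state before outcome data are reviewed which recorded cleansing grades count as sufficient quality for the primary endpoint. Add a sensitivity analysis that scores Fair studies the other way where every other condition of the endpoint is met.

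The rule will have no control-arm counterpart for the colon, and the protocol should say so. Quality grades are defined for MR enterography, but none is defined for ileocolonoscopy or small bowel capsule endoscopy. Applying a threshold to MR enterography alone would not restore symmetry and is not suggested.

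The cost is aligned wording in two sections, one sentence on scoring and one extra analysis. The cleansing grade is already part of the CE report, so no new data are needed. The downside is that observed CE completeness may be lower if Fair studies are not counted.

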### **Ileocolonoscopy**

Bowel cleansing and IC is performed according to standard clinical practice and local preferences. The following bowel cleansing regimen is an example used at several participating institutions:

Picoprep 10 mg + 3.5 g + 12 g (or Citrafleet 10 mg + 3.5g + 11g):

1 sachet ingested at 6 PM the day before IC followed by 1-2 liters of water

1 sachet ingested at 6 AM on the day of IC followed by 1-2 liters of water

A full colonoscopy is documented by identifying two of the following: Visualization of the appendicular orifice, tri-angular fold or intubation of the terminal ileum. Intubation of the terminal ileum is documented with a biopsy or a photo showing intestinal villi. The length of terminal ileum intubation is estimated and the reason for an unsuccessful intubation is recorded. The Simple Endoscopic Score for Crohn's Disease (SES-CD) assesses the disease severity. Photo- and video documentation of relevant findings is secured.

### *Findings at IC consistent with CD:*

- Multiple (> 3) erosions or aphthous ulcers
- Irregular ulcers or fissures
- Cobblestone pattern
- Luminal narrowing because of inflammation and/or fibrous stenosis

### **Histopathology**

The histological assessment is performed by pathologists at the participating centers. Biopsies are cut,

stained with hematoxylin and eosin and examined under a standard light microscope. The assessment is based on the following lesions:

- 1) Architectural and surface distortion: Ulceration/erosion, crypt irregularity, mucosal atrophy, mucin depletion.
- 2) Signs of chronic inflammation: Lamina propria chronic inflammation with lymphocytes and plasma cells, basal plasmacytosis, eosinophilic inflammation, epithelioid cell granulomas.
- 3) Signs of acute inflammation: Epithelial and lamina propria acute inflammation with neutrophil granulocytes, cryptitis, crypt abscesses and crypt destruction granulomas.

*Findings at histopathology consistent with CD:*

For surgical specimens, it has been suggested that CD is diagnosed when 3 features are present in the absence of granulomas or when granulomas are present with one 1 extra feature. Most experts agree that the same definition could be applied to endoscopic biopsies, i.e. epithelioid cell granulomas plus crypt irregularity and/or chronic inflammation is suggestive of CD. The distribution of inflammatory lesions also supports a specific diagnosis – segmental inflammation in CD versus continuous inflammation in UC.

### **Small bowel capsule endoscopy**

SBCE is performed with the Pillcam SB3 (Medtronic, Dublin, Ireland) according to standard clinical practice after fasting and, if preferred by the IBD center, with prior bowel preparation (polyethylene glycol). SBCEs are analyzed by a specialist in gastroenterology with capsule endoscopy experience. The PillCam Reader Software from Medtronic is used for the analysis. Findings are reported standardized according to the *Capsule Endoscopy Minimal Standard Terminology* (CEMST). It is recorded whether the capsule reaches the colon. The transit times through the stomach and small intestine are recorded. Pathological findings are localized according to the time interval after capsule ingestion and the usual landmarks. The small intestine is divided into thirds based on the passage time. Disease severity in the small bowel is assessed with the Lewis score.

*Findings at SBCE consistent with CD:*

- Multiple (> 3) erosions or aphthous ulcers
- Irregular ulcers or fissures
- Cobblestone pattern
- Luminal narrowing because of inflammation and/or fibrous stenosis

## MR enterography

MRE with oral and intravenous contrast is performed as per local protocol at the participating centers. An example protocol is provided below:

Patients attend the Department of Radiology fasting and 1.5 hours before the examination. 1 L of Mannitol 7.5% solution is ingested 1.5 hours before the examination. 20 mg Buscopan (hyoscine butylbromide) is administered intravenously to reduce artifacts from bowel peristalsis. Images are recorded with coronal T2, B-FFE, T1, SPIR and axial T1w sequences. Gadolinium 0.1 mmol/kg is administered intravenously for post contrast assessment. In addition, a diffusion weighted sequence is performed. The patient is observed in the radiology department for 30 minutes after the procedure. Driving is prohibited for 4 hours because of accommodation disturbances secondary to Buscopan administration.

Radiologists analyze MREC at the participating centers. Radiologists are not blinded to the clinical information. Pathological findings are localized according to the estimated distance from the ileocecal valve or another fixed point. The small intestine is divided into thirds (proximal, middle and distal third) and the colon is divided into five segments: Cecum, ascending colon, transverse colon, descending/sigmoid colon and rectum. Findings are reported in a standardized fashion, and the treating gastroenterologist is provided with a report stating whether MREC is consistent with CD, the localization and severity, and the presence of disease complications. Images will be saved digitally on the local and regional picture archiving and communications system (PACS). The assessment is based on the following definitions:

### *Intestinal distension:*

- Good distension (> 75% of the intestine is sufficiently distended)
- Adequate distension (50-75% of the intestine is sufficiently distended)
- Poor distension (< 50% of the intestine is sufficiently distended)

### *Image quality:*

- Good (diagnostic images without artifact)
- Sufficient (diagnostic images with artifacts)
- Poor (non-diagnostic images)

### *Findings at MRE consistent with CD:*

- Early or minimal disease
  - Superficial ulcerations

- Transmural disease
  - Deep ulcers
  - Cobblestone pattern
  - Post-contrast enhancement (the relative contrast enhancement (RCE) is recorded)
  - Wall thickening > 3 mm (the maximum wall thickness is recorded)
  - Stenosis (the relative change of the intestinal caliber (%), stricture grade and occurrence of prestenotic dilation is recorded)
    - *Definition of small bowel stenosis:* > 50% reduction of the intestinal lumen compared to the adjacent small intestine. *High-grade stenosis* is defined by the presence of prestenotic dilation > 2.5 cm and/or collapse of the distal segment.
    - *Definition of colonic stenosis:* > 20% reduction of the intestinal lumen compared to the adjacent colon. *High-grade stenosis* is defined by an intestinal lumen < 11 mm, prestenotic dilation > 2.5 cm and/or collapse of the distal segment.
- Extraintestinal disease:
  - Creeping fat
  - Dilated vasa recta (Comb sign)
  - Enlarged lymph nodes (> 5 mm)
  - Fistula
  - Abscess
- *Ileocolonic disease severity assessed with MaRIA:*
  - Ulcer healing < 11
  - Mucosal healing < 7

